## 9.11. Selection of Investigators

Surgeons who are qualified by training (board certified in otolaryngology in accordance with USand hospital guidelines), education, and relevant experience appropriate to the use of the product and associated procedures will be considered for participation as investigators in this study. Investigators/sites must have adequate time and resources to conduct the study throughout the duration of the study and have access to an adequate number of eligible subjects. Investigators/sites must be able to comply with applicable Institutional Review Board (IRB) and regulatory requirements. Investigator must not be debarred, disqualified, or working under sanctions in applicable regions. Qualifications are verified through valid CV and current licensing and maintained with study documentation.

MDT17024BZP

Version 5.0 (18 MAR 2019)

Page 29 of 47

Medtronic

#### 10. Risks and Benefits

#### 10.1.Potential Risks

#### 10.1.1. Risks of Investigational Medical Device

The potential risks associated with the standard tonsillectomy procedure include but are not limited to: reaction to anesthesia, swelling, bleeding, infection (including fever), nausea, vomiting, dehydration, velopharyngeal incompetence, and pain.

The potential risks associated with BiZact™ include: unintended cutting, bruising, tearing, thermal burns, or other damage to tissue, arcing, pinching, inadequate/no seal, pain, bleeding, nausea, vomiting, and headache. There is also a risk of electromagnetic interference if the patient has an implantable electronic device.

In the event of unacceptable bleeding, investigators may use alternate means to achieve acceptable hemostasis, just as they would in a typical tonsillectomy procedure. Subjects in the study will be given instruction as to what to do in the event of post-operative bleeding in order to minimize any adverse effects.

The risk analysis is based on the operation of BiZact™ by trained personnel. The overall residual risk after design risk mitigation strategies and/or design control was deemed acceptable for the BiZact™ system.

The instructions for use (IFU) provide instructions on proper use of the device along with warnings and precautions to mitigate risk of misuse and notify the surgeon of potential risks. Surgeons will undergo training on the device prior to participation in the study.

Reproductive and developmental toxicology studies in animals to evaluate the potential for AEs on reproductive ability and effects on the embryo/fetus have not been conducted. As with any device, there is always a risk of a rare or previously unknown side effect developing from the treatment or use of the device.

#### 10.2.Potential Benefits

The potential benefits associated with BiZact™ device usage include, but are not limited to: reduction in pain, blood loss, time to return to normal diet, and activity post tonsillectomy procedure as compared to conventional tonsillectomy; however, there may be no benefits at all.

#### 10.3. Risk Benefit Rationale

Post-operative pain and delayed time to normal diet and activity are common challenges after tonsillectomy procedures. Aside from conventional cold steel and electrocautery dissection, the introduction of numerous energy based tools and techniques allow for the simultaneous dissection and sealing of vessels significantly improving safety and reducing the complications of the procedure (1-3). In most cases however, these energy based devices use heat to establish hemostasis (arrest of bleeding), which can lead to lateral heating and damage to adjacent structures delaying wound healing and increasing post-operative pain (4). Thus, the use of the investigational medical device for

MDT17024BZP

Version 5.0 (18 MAR 2019)

Page 30 of 47

Medtronic

tonsillectomy presents a similar risk profile and minimal if any increase in risk over other commonly used devices.

A positive risk/benefit ratio has been demonstrated with BiZact™ as evidenced by preclinical and biocompatibility testing, and a multicenter adult tonsillectomy is currently underway. There were no apparent adverse systemic or local effects in any of the preclinical studies using animal models. BiZact™ is based off Ligasure™ technology which historically has been shown to be safe and effective for tonsillectomy procedures providing adequate hemostasis (arrest of bleeding) while minimizing postoperative pain.

The product design, as well as the results of internal studies, support BiZact™ as a class 2 FDA cleared for use in adult patients. It is CE-mark and Therapeutic Goods Administration (TGA) Licensed product for use in adult and pediatric patients. There are currently no known interactions between the BiZact™ device and concurrent medical interventions.

#### 11. Adverse Events and Device Deficiencies

Adverse event (AE) definitions used in this study are based on ISO 14155:2011 (Clinical Investigation of Medical Devices for Human Subjects -- Good Clinical Practice).

All AEs and Device Deficiencies will be collected and documented a and Day 0 (after commencement of surgery with BiZact™ to 28 (+7) days follow-up. Device Deficiencies not related to an adverse event (e.g. damaged out of the box) will be collected from when they are first noticed, regardless of usage in a case.

#### 11.1.Definitions and Classifications

#### 11.1.1. Adverse Event (AE)

In alignment with ISO 14155:2011 (Section 3.2), an Adverse Event is any untoward medical occurrence, unintended disease or injury, or untoward clinical signs (including abnormal laboratory findings) in subjects, users or other persons, whether or not related to the investigational medical device.

This definition includes events related to the investigational medical device and the procedures involved. For users or other persons, this definition is restricted to events related to investigational medical devices.

Adverse Events may include but are not limited to bleeding, tissue injury, and thermal burns.

For study purposes, the following occurrences are considered to be expected observations following surgical procedures (primarily associated with anesthesia) and will not be considered reportable AEs, as long as the event is not associated with significant sequelae, does not prolong hospitalization, and responds to standard medical therapy:

- Postoperative transient nausea determined to be procedure related within the first 24 postoperative hours.
- Postoperative transient emesis determined to be procedure related within the first 24 postoperative hours.

MDT17024BZP

Version 5.0 (18 MAR 2019)

Page 31 of 47

Medtronic

- Postoperative constipation, determined to be procedure and/or medication related for the duration of medication administration for management of pain.
- Postoperative pain that the Investigator considers common and within normal limits for the procedure and is well-managed with medication. Pain that the Investigator considers outside normal, or is not well-managed with medication, as well as pain that severe (score 7 or higher) and ongoing at the end of the study will be captured as an adverse event.

Additionally, the following should not be considered an AE:

- A condition requiring a preplanned procedure unless the condition worsened since enrollment
- A preexisting condition found as a result of screening, unless the condition has worsened since enrollment.

All responses to the above events that require treatment beyond the institution's standard procedures will be reported as AEs.

All AEs observed during the course of this study, regardless of severity or relationship to the device will be recorded on the appropriate eCRF. Adverse events regardless of relatedness will be treated per standard of care at each institution. For example, the management of pain or bleeding will be at the discretion of the treating physician, as he or she is monitoring the patient's condition.

#### 11.1.2. Serious Adverse Events (SAE)

In alignment with ISO 14155:2011 (Section 3.37), a serious adverse event (SAE) is any AE that has:

- led to death.
- led to serious deterioration in the health of the subject that either resulted in
  - o a life-threatening illness or injury, or
  - o a permanent impairment of a body structure or a body function, or
  - o in-patient or prolonged hospitalization, or
  - medical or surgical intervention to prevent life threatening illness or injury or permanent impairment to a body structure or a body function, or
- led to fetal distress, fetal death, or a congenital abnormality or birth defect.

NOTE: Planned hospitalization for a pre-existing condition or a procedure required by the clinical investigational plan, without serious deterioration in health, is not considered an SAE.

#### 11.1.3. Adverse Device Effect (ADE)

In alignment with ISO 14155:2011 (Section 3.1), an Adverse Device Effect is an adverse event related to the use of an investigational medical device.

This definition includes adverse events resulting from insufficient or inadequate instructions for use, deployment, implantation, installation, or operation, or any malfunction of the investigational medical device.

This definition includes any event resulting from use error or from intentional misuse of the investigational medical device.

Adverse Device Effects will be reported by the Investigator(s). If escalation is required (due to the potential need for reporting) ADEs will be reviewed by Medtronic Medical Affairs. Both confirmed and

MDT17024BZP

Version 5.0 (18 MAR 2019)

Page 32 of 47

possible device related events will be included in the study report. ADE(s) may be anticipated or unanticipated (UADE).

Examples of adverse device effects include but are not limited to: unintended cutting, unintended electrical path, or arcing.

#### 11.1.4. Serious Adverse Device Effect (SADE)

In alignment with ISO 14155:2011 (Section 3.36), a Serious Adverse Device Effect is an adverse device effect that has resulted in any of the consequences characteristic of a serious adverse event.

#### 11.1.5. Unanticipated Serious Adverse Device Effect (USADE)

In alignment with ISO 14155:2011 (Section 3.42), an Unanticipated Serious Adverse Device Effect is a serious adverse device effect which by its nature, incidence, severity, or outcome has not been identified in the current version of the risk analysis report.

NOTE: Anticipated serious adverse device effect (ASADE) is an effect which by its nature, incidence, severity or outcome has been identified in the risk analysis report.

#### 11.1.6. Adverse Event Severity Classification

Severity will be defined according to the following criteria:

Mild	Awareness of event, but easily tolerated
Moderate	Discomfort enough to cause some interference with activities of daily living (ADL)
Severe	Incapacitating, with an inability to perform ADL
Death	Death related to AE

An AE can be classified as severe and not deemed an SAE. Similarly, an SAE is not automatically severe in nature.

#### 11.1.7. Adverse Event Relationship Classification

Causality assessments define the relationship between the use of the medical device (including the medical-surgical procedure) and the occurrence of each adverse event, according to MEDDEV (Guidelines on Medical Devices, Clinical Investigations: Serious Adverse Event Reporting). The presence of confounding factors, such as concomitant medication/treatment, the natural history of the underlying disease, other concurrent illness or risk factors shall also be considered.

Each AE will be classified according to five different levels of causality. The sponsor and the investigators will use the following definitions to assess the relationship of the serious adverse event to the investigational medical device or procedures:

*Not related*: relationship to the device or procedures can be excluded when:

- 1. the event is not a known side effect of the product category the device belongs to or of similar devices and procedures
- 2. the event has no temporal relationship with the use of the device or the procedures;
- 3. the serious event does not follow a known response pattern to the medical device (if the response pattern is previously known) and is biologically implausible;

MDT17024BZP

Version 5.0 (18 MAR 2019)

Page 33 of 47

Medtronic

- 4. the discontinuation of medical device application or the reduction of the level of activation/exposure when clinically feasible and reintroduction of its use (or increase of the level of activation/exposure), do not impact on the serious event;
- 5. the event involves a body-site or an organ not expected to be affected by the device or procedure;
- 6. the serious event can be attributed to another cause (e.g. an underlying or concurrent illness/clinical condition, an effect of another device, drug, treatment or other risk factors);
- 7. the event does not depend on a false result given by the device used for diagnosis, when applicable;
- 8. harms to the subject are not clearly due to use error;
- 9. In order to establish the non-relatedness, not all the criteria listed above might be met at the same time, depending on the type of device/procedures and the serious event.

Unlikely: the relationship with the use of the device seems not relevant and/or the event can be reasonably explained by another cause, but additional information may be obtained.

Possible: the relationship with the use of the device is weak but cannot be ruled out completely. Alternative causes are also possible (e.g. an underlying or concurrent illness/ clinical condition or/and an effect of another device, drug or treatment). Cases were relatedness cannot be assessed or no information has been obtained should also be classified as possible.

Probable: the relationship with the use of the device seems relevant and/or the event cannot be reasonably explained by another cause, but additional information may be obtained.

Causal relationship: the serious event is associated with the device or with procedures beyond reasonable doubt when:

- 1. the event is a known side effect of the product category the device belongs to or of similar devices and procedures;
- 2. the event has a temporal relationship with device use/application or procedures;
- 3. the event involves a body-site or organ that
  - a. the device or procedures are applied to;
  - b. the device or procedures have an effect on;
- 4. the serious event follows a known response pattern to the medical device (if the response pattern is previously known);
- the discontinuation of medical device application (or reduction of the level of activation/exposure) and reintroduction of its use (or increase of the level of activation/exposure), impact on the serious event (when clinically feasible);
- 6. other possible causes (e.g. an underlying or concurrent illness/ clinical condition or/and an effect of another device, drug or treatment) have been adequately ruled out;
- 7. harm to the subject is due to error in use;
- 8. the event depends on a false result given by the device used for diagnosis, when applicable;
- 9. In order to establish the relatedness, not all the criteria listed above might be met at the same time, depending on the type of device/procedures and the serious event.

The Sponsor and the Investigators will distinguish between the serious adverse events related to the device and those related to the procedures (any procedure specific to the clinical investigation). An adverse event can be related both to procedures and the device. Complications of procedures are considered not related if the said procedures would have been applied to the subjects also in the absence of device use/application.

MDT17024BZP

Version 5.0 (18 MAR 2019)

Page 34 of 47

In some particular cases, the event may be not adequately assessed because information is insufficient or contradictory and/or the data cannot be verified or supplemented. The sponsor and the Investigators will make the maximum effort to define and categorize the event and avoid these situations. Where the sponsor remains uncertain about classifying the serious event, it should not exclude the relatedness and classify the event as "possible".

Particular attention shall be given to the causality evaluation of unanticipated serious adverse (device) events. The occurrence of unanticipated events related to the use of the device (USADE) could suggest that the clinical investigation places subjects at increased risk of harm than was to be expected beforehand.

#### 11.1.8. Adverse Event Outcome Classification

Outcome of the event will be defined according to the following:

- *Fatal*: This event is determined to be the cause of death.
- **Not Recovering/Not Resolved**: The event has retained pathological conditions resulting from the prior disease or injury.
- Recovered/Resolved: The event has fully resolved at the end of the study.
- Recovering/Resolving: The event is ongoing at the end of the study.
- *Unknown*: The event has been unclassified at the end of the study.

#### 11.2.Reporting of Adverse Events

The following events are generally considered reportable during the course of this study and should be reported to the sponsor:

- any ADE, SADE, SAE, or USADE
- any Device Deficiency that might have led to an SADE if
  - o suitable action had not been taken or
  - o intervention had not been made or
  - o circumstances had been less fortunate
- new findings/updates in relation to already reported events.

Events will be reviewed by the sponsor to determine any reporting obligations to regulatory bodies and IRBs/ECs.

MDT17024BZP

Version 5.0 (18 MAR 2019)

Page 35 of 47

The following table captures the reporting requirements for this study. Local and regional regulatory requirements shall be followed in addition to study requirements.

Type of Event	Timeframe	Submit to	Other Reporting Requirements
AE	As soon as possible but no more than 10 working days after the day that you become aware of information from any source, that reasonably suggests that an AE has occurred	Sponsor/ Device Manufacturer	
Any Death	As soonas practicable but no more than 10 work days after the day that you become aware of information from any source, that reasonably suggests that a device has or may have caused or contributed tothe death of a patient of your facility	Sponsor/ Device Manufacturer and Local (IRB/ EC) and regional regulators (FDA)	
UADE	As soon as possible, but in no event later than 10 working days afterthe investigator first learns of the effect.	Sponsor / Device Manufacturer and any local/ regionally required regulators	
All Serious Events including SAEs, USADEs, Serious Injuries or Significant Safety Issues	Within 24 hours, but no later than 10 work days (and/or per local requirements) after the day that investigator becomes aware of information, from any source, that reasonably suggests that a device has or may have caused or contributed to a serious injury to a patient of your facility.	Sponsor / Device Manufacturer and as per local reporting requirements.	

MDT17024BZP Version 5.0 (18 MAR 2019) Page 36 of 47

#### 11.3. Adverse Event Recording

All observed adverse events (ADEs, UADEs and SAEs) will be collected and documented at the time of surgery to 28 (+7) days follow-up. If the adverse event is recorded at the last subject visit and considered serious and device-related, the event should be followed for resolution for up to seven (7) days, or until the resolution of the event, whichever is earliest, even if this falls outside the 28 (+7) day visit window. To ensure consistency of data collection no new events will be recorded after the 28 (+7) day visit window, even if the subject is being followed for resolution of another event. If the adverse event is ongoing at the end of the study, and exceeds the follow up time frame, the patient will continue to receive standard care with their normal physician, and the event will be listed as ongoing.

Assessment of the occurrence of an AE will be based on changes in the subject's physical examination, laboratory results and/or signs and symptoms. Adverse events will be monitored until a subject completes the study unless the Investigator determines the event is related to the device, in which case they will be monitored until resolution if possible. Medical care will be provided, as defined in the informed consent, for any AE related to study participation. Adverse events will be collected on an AE eCRF and applicable source documentation. To the extent possible, the event to be recorded and reported is the event diagnosis as opposed to event symptoms (e.g., fever, chills, nausea and vomiting in the presence of a clinically diagnosed infection is to be reported as infection only). For the purposes of this protocol, only those AEs occurring after enrollment and the commencement of the tonsillectomy with the study device will be recorded.

#### 11.5. Device Deficiencies

In alignment with ISO14155:2011 (Section 3.15), a Device deficiency is an inadequacy of a medical device related to its identity, quality, durability, reliability, safety or performance, such as malfunction, misuse or use error and inadequate labeling.

MDT17024BZP

Version 5.0 (18 MAR 2019)

Page 37 of 47

All BiZact™ device deficiencies will be documented on the Device Malfunction eCRF and the device should be returned to Medtronic for analysis, if possible. Instructions for returning the device will be provided. Device deficiencies should also be documented in the subject's medical record.

Device deficiencies are NOT to be reported as AEs. However, if there is an AE that results from a device deficiency, that specific event would be recorded on the eCRF.

### 12. Data Review Committees

There will be no use of data review committees in this study. Instead, a steering committee and a safety review committee will monitor the trial's progress including trends of data over time and scientific relevance of the data collected. Please see section 15.10. These groups will provide oversight in terms of scientific validity and the safe conduct of the study.

By nature, this study's focus is about the amount of intraoperative bleeding, which is expected to be low due to the nature of the procedure and the currently available date. Additionally, this is a study of 3 sites and 60 subjects, with no planned interim analysis, and as such, has a lower burden in terms of severity of implications, and degree of data review and analysis compared to a larger study with interim data review needs or a study focusing on severe complications or mortality. Per FDA guidance (OMB Control No 0910-0581 "The Establishment and Operation of Clinical Trial Data Monitoring Committees for Clinical Trial Sponsors" DMCs are "generally recommended for any controlled trial of any size that will compare rates of mortality or major morbidity, but a DMC is not required or recommended for most clinical studies." The guidance goes on to list conditions wherein a DMC may offer additional protections to study participants. Apart from the use in pediatric population, this study does not meet any of the criteria listed wherein a DMC would provide added benefit. Even within this population, the study is small and of short planned duration, so it is unlikely that a DMC would be able to provide added or more rapid benefit than the steering committee or safety review mechanisms.

## 13. Statistical Design and Methods

### 13.1. Statistical Test Methods

Continuous variables will be summarized using counts, means, standard deviations, medians, minimum and maximum. Categorical variables will be summarized using frequencies and percentages. Changes to the planned statistical analysis as defined in the protocol will be documented in the statistical analysis plan and clinical study report.

## 13.2. Sample Size Determination

The analysis technique will be a 1-sample t-test (or Wilcoxon ranked sign if nonparametric test is desired), with a one-sided type I error rate ( $\alpha$ ) of 0.025. A sample size of 60 subjects is selected to ensure that multiple surgeons participate and to create an opportunity for a range of subject ages to be enrolled. Statistical power for a sample size of 60 subjects exceeds 99%.

MDT17024BZP

Version 5.0 (18 MAR 2019)

Page 38 of 47

Medtronic

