#### **Statistics**

The analysis technique will be a 1-sample t-test (or Wilcoxon ranked sign if nonparametric test is desired), with a one-sided type I error rate ( $\alpha$ ) of 0.025. A sample size of 60 is selected to ensure that multiple surgeons participate and to create an opportunity for a range of subject ages to be enrolled. Statistical power for a sample size of 60 exceeds 99%.

The primary hypotheses of this study are:

H0: Mean intra-operative blood loss = 31 mL HA: Mean intra-operative blood loss < 31 mL

The performance goal of 31 mL derives from a meta-analysis comparing modern technology to conventional techniques (i.e. electrocautery and cold steel) (Alexiou *et al.* 2011). This paper included a total of 3139 patients included in thirty-three published studies. The values from all of the studies that reported intra-operative bleeding were combined to calculate a mean blood loss. This value encompasses a variety of techniques and technologies and a number of different studies to capture a realistic value for comparison.

Intraoperative blood loss during tonsillectomy with BiZact™ is expected to be low. The expected mean value for the BiZact™ device is a conservative estimate derived from data for LigaSure™ and other vessel sealing systems in the Alexiou meta-analysis. The expected standard deviation is the average of the standard deviation values for all studies that reported blood loss in the meta-analysis.

Expected mean for BiZact™: 10 mL Expected standard deviation: 15.1 mL

Additionally, descriptive statistics for blood loss will be reported for different age groups (ages 2-5 and ages 6-12) as well as for different sites, surgeons, and countries.

Secondary endpoints will be evaluated with descriptive statistics. For continuous variables, the mean, median, and standard deviation will be reported, along with a 95% confidence interval for the mean where appropriate.

For categorical data, proportions will be reported, along with 95% confidence intervals where appropriate.

MDT17024BZP Version 5.0 (18 MAR 2019)

Page 13 of 47

Medtronic

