#### 5.2. Endpoints

#### 5.2.1. Primary Endpoint

The primary endpoint of this study is the amount of intra-operative blood loss. The study will be considered a success if the mean intra-operative blood loss is less than the mean intra-operative blood loss associated with conventional tonsillectomy in a large meta-analysis (7). See the Statistical Design and Methods (Section 13) for additional details.

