## 13.4. Statistical Analysis Endpoints

### 13.4.1. Primary Endpoint

The primary hypotheses of this study are:

H0: Mean intra-operative blood loss =31 mL HA: Mean intra-operative blood loss < 31 mL

The analysis technique will be a 1-sample t-test, with a one-sided type I error rate ( $\alpha$ ) of 0.025. If intraoperative blood loss data appear to be non-normally distributed (as evidenced by p < 0.05 from a Shapiro-Wilk test), a Wilcoxon signed rank test will also be conducted.

The performance goal of 31 mL derives from a meta-analysis comparing modern technology-assisted to conventional tonsillectomy (i.e. electrocautery and cold steel) (7). This paper included a total of 3,139 patients included in thirty-three published studies. The values from the studies that reported intra-operative bleeding were combined to calculate a mean blood loss. This value encompasses a variety of techniques and technologies and a number of different studies to capture a realistic value for comparison.

Intra-operative blood loss during tonsillectomy with BiZact™ is expected to be low. The expected mean value for the BiZact™ device is a conservative estimate derived from data for LigaSure™ and other vessel sealing systems in the Alexiou meta-analysis (7). The expected standard deviation is the average of the standard deviation values for all studies that reported blood loss in the meta-analysis.

Expected mean intra-operative blood loss for BiZact™: 10 mL Expected standard deviation: 15.1 mL

Additionally, descriptive statistics for blood loss will be reported for different age groups (ages 2-5 and ages 6-12) as well as for different sites, surgeons, and countries.

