## 13.8. Poolability of Results

Poolability of blood loss data will be assessed for each of the participating investigational sites. Descriptive statistics will be reported separately by site. A one-way ANOVA will test whether there is evidence of a difference in mean blood loss between sites. If this test does not suggest a difference (p-value  $\geq 0.15$ ), data will be pooled across sites for inference (i.e., for the primary hypothesis test and 95% confidence interval for mean blood loss). If there is evidence of a difference (p < 0.15 from the one-way ANOVA), confidence intervals will be presented separately for each site, and p-values from the hypothesis test in Section 8.4.1 will also be calculated separately for each site. For full details on the planned analysis and poolability, see Statistical Analysis Plan (SAP).

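### The plan gives two conflicting roles for the Wilcoxon test and never says which test decides success on a hypothesis about the mean

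*Combined protocol and SAP*

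**What the plan says.** The rule for the primary test appears three times, in two forms.

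- **Section 13.2, Sample Size Determination:** "The analysis technique will be a 1-sample t-test (or Wilcoxon ranked sign if nonparametric test is desired". The Wilcoxon may stand in for the t-test, and the only condition is that someone wants it.
- **Synopsis, Statistics:** the same option, "or Wilcoxon ranked sign if nonparametric test is desired".
- **Section 13.4.1, Primary Endpoint:** "The analysis technique will be a 1-sample t-test, with a one-sided type I error rate", with no alternative named. If the data look non-normal, "as evidenced by p < 0.05 from a Shapiro-Wilk test", then "a Wilcoxon signed rank test will also be conducted". Here the Wilcoxon is an addition with a defined trigger.

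The target is the mean throughout. Section 13.4.1 sets the null hypothesis at a mean of 31 mL and the alternative below it, at a one-sided level of 0.025. Section 5.2.1 reads: "The study will be considered a success if the mean intra-operative blood loss is less than" the mean for conventional tonsillectomy in the cited meta-analysis. It names no test.

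Section 13.8 refers to a single primary hypothesis test but does not name it. For the by-site analysis it says "p-values from the hypothesis test in Section 8.4.1 will also be calculated separately for each site". Section 8.4 is the list of exclusion criteria, so the pointer leads nowhere. Section 13.8 also refers to a SAP for full details. No separate SAP text was available, so this point covers the protocol text only.

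**The concern.** The two forms differ in role (instead of, or in addition to) and in trigger (discretion, or a Shapiro-Wilk result). A rule that applies if desired leaves the choice of primary test open after the data are seen. This is an unblinded single-arm study whose data go to FDA for a pediatric indication (Sections 4.2 and 6.2).

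The choice also changes what is tested. The t-test addresses the mean. The signed-rank test addresses a different centre, the middle of all pairwise averages, which equals the mean only when the distribution is symmetric. For right-skewed blood loss it lies below the mean, so the Wilcoxon can reject when the mean is not below 31 mL. If the Wilcoxon may decide success, or if either test may, the stated 0.025 level for a claim about the mean does not hold under skew.

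**Working it through.** **Inputs.** From Sections 13.2 and 13.4.1: n = 60, one-sided level 0.025, goal 31 mL, expected mean 10 mL, expected SD 15.1 mL, Shapiro-Wilk threshold 0.05. The distribution shapes (normal, gamma, lognormal) are assumptions.

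**Step 1: the plan's power.** Noncentrality = (31 − 10)/15.1 × √60 = 10.77 with 59 degrees of freedom. Power exceeds 0.9999, so the stated figure of more than 99% is reproduced. Twelve children would already give 99.2%.

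**Step 2: is skew likely?** Blood loss cannot be negative. A normal model with mean 10 and SD 15.1 puts Φ(−10/15.1) = Φ(−0.66) = 25% of children below 0 mL, so the planning values imply right skew. In 3,000 simulated trials per shape at these values, Shapiro-Wilk was significant in essentially every gamma and lognormal trial. The second test would very probably be run.

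**Step 3: which SD to use at the null.** Section 13.4.1 says: "The expected standard deviation is the average of the standard deviation values for all studies that reported blood loss" in the meta-analysis. It is not specific to vessel-sealing devices, so 15.1 mL is kept at a mean of 31 mL. The shapes are then:
- Gamma: shape (31/15.1)² = 4.21, scale 15.1²/31 = 7.36.
- Lognormal: log-variance ln(1 + (15.1/31)²) = 0.213, so the median is 31/√1.237 = 27.9 mL although the mean is 31 mL.

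**Step 4: false success at a true mean of 31 mL (nominal 2.5%).** There were 20,000 trials per scenario. The Shapiro-Wilk and either-test columns use 4,000 of them. The either-test column counts success on the t-test, or on the Wilcoxon when Shapiro-Wilk rejects.

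| Data | t-test | Wilcoxon | Shapiro-Wilk p < 0.05 | Either test |
|---|---|---|---|---|
| Normal | 2.3% | 2.3% | 4.5% | 2.5% |
| Gamma | 3.7% | 9.1% | 76.6% | 8.5% |
| Lognormal | 4.5% | 15.4% | 93.7% | 15.4% |

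A separate run of 10,000 trials per scenario gave, for t-test, Wilcoxon and either test: normal 2.7%, 2.6%, 2.7%; gamma 3.6%, 9.5%, 9.0%; lognormal 4.4%, 15.1%, 15.0%. In that run, letting the Wilcoxon replace the t-test after a significant Shapiro-Wilk gave the same rates as the either-test rule for both skewed shapes. Requiring both tests gave the t-test rates.

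**Step 5: how often the tests disagree (SD 15.1).**

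| True mean (mL) | Gamma | Lognormal |
|---|---|---|
| 10 | 0.0% | 0.3% |
| 15 | 0.0% | 0.2% |
| 20 | 0.2% | 1.1% |
| 25 | 10.9% | 15.8% |
| 28 | 19.8% | 30.6% |

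At 25 and 28 mL virtually every disagreement is a Wilcoxon success with a t-test failure, so the ambiguity favours declaring success.

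**Sensitivity to the SD at the null.** With an assumed SD of 20 mL the Wilcoxon false-success rate is 13% (gamma) to 23% (lognormal); with 31 mL it is 25% to 42%. Nothing in the protocol supports these larger SDs, and the conclusion does not rest on them.

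**The case against.** The strongest reply is that Section 13.4.1 is the operative text. It states the hypotheses on the mean, names the t-test without an alternative, and brings in the Wilcoxon only as an extra. Section 13.8 speaks of one primary test alongside a confidence interval for the mean. On this reading the defect is a loose parenthesis in the synopsis and the sample-size section, and no sentence says that success on either test suffices. This is the natural reading of 13.4.1 taken alone. But 13.4.1 does not say that the t-test decides, and two other places expressly allow substitution.

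Other points stand in part:

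- The separate SAP may settle the matter. If so, the protocol would still contradict itself.
- Skew at the null is assumed. With mean 31 and SD 15.1 a normal model puts only about 2% of children below 0 mL (31/15.1 = 2.05 SDs), so the planning figures do not force marked skew there. The fair range for the Wilcoxon therefore starts at 2.3%, under normality.
- The t-test itself runs at 3.7% to 4.5% under the assumed skew. Making it decisive reduces the excess and matches the hypothesis, but does not guarantee 0.025.
- The wrong section number in 13.8 is probably left over from the renumbering recorded in the version history. It is a minor error, but it means that 13.8 does not resolve the question.

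**Conclusion.** The concern holds. The protocol states two incompatible rules for the Wilcoxon test and does not name the test that decides success. If the Wilcoxon can decide, the chance of declaring success at a true mean of 31 mL is about 9% to 15% for gamma to lognormal data with SD 15.1 mL, against the stated 2.5%; if the data are normal there is no inflation. The size rests on the assumed shapes and on using the planning SD at the null. The contradiction itself rests on the text alone.

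The practical reach is limited. The tests disagree in at most 1.1% of simulated trials at the true means of 10, 15 and 20 mL, and the sample size and power statement are unaffected. It should still be fixed, because the error rate is defined at the 31 mL goal and this is the primary analysis of a pivotal study.

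**What to change.** 1. In the synopsis and Section 13.2, delete the parenthesis that offers the Wilcoxon, so that both match Section 13.4.1.
2. Add to Section 13.4.1: *Study success is determined only by the one-sample t-test of the mean. Any Wilcoxon result is supportive and can neither establish nor overturn success.*
3. In Section 13.8, change the pointer from Section 8.4.1 to Section 13.4.1, so that the by-site p-values come from the same test.
4. Carry the sentence in item 2 into the SAP.

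The cost is wording only. Sample size and data collection do not change. Power is kept: at mean 10 mL, SD 15.1 mL and n = 60 the t-test alone succeeds in 99.7% (lognormal) to 100% (gamma) of simulated trials. The change removes the ambiguity and aligns the deciding test with the hypothesis. It does not remove the modest excess of the t-test over 0.025 under skew.
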